1 OVERVIEW AND INVESTIGATIONAL PLAN

1.1 STUDY DESIGN AND RANDOMIZATION

Multinational, randomized, double-blind, placebo-controlled, parallel groups (2 groups), 52-week Phase 3 study to assess the efficacy, safety, and tolerability of dupilumab in patients with moderate-to-severe type 2 inflammatory COPD such as that driven by activation of IL-4, IL-5, and IL-13 on an established LABA, LAMA and/or ICS background therapy (triple therapy unless ICS contraindicated). Study treatments are dupilumab 300 mg q2w or placebo q2w administered during the 52-week treatment period.

After a run-in period of 4 weeks \pm 1 week, patients will be centrally randomized using a permuted block randomization schedule via Interactive Voice Response System/Interactive Web Response System (IVRS/IWRS) in a 1:1 randomization ratio for dupilumab 300 mg q2w and a matching placebo q2w for SC administration. Randomization will be stratified by country, by ICS dose (high dose ICS [yes/no]) at baseline, and smoking status at screening (current smokers or not). Enrollment will be capped at 30% current smokers (as defined by smoking status at screening visit).

A total of approximately 924 patients with COPD will be randomized to two treatment arms (462 patients/arm).

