2.1.4.1 Adverse events variables

Adverse event observation period

- Pretreatment adverse events are adverse events that developed or worsened or became serious during the screening epoch
- Treatment-emergent adverse events are adverse events that developed or worsened or became serious during the treatment-emergent adverse event period
- Posttreatment adverse events are adverse events that developed or worsened or became serious during the posttreatment epoch.

All adverse events (including serious adverse events and adverse events with pre-specified monitoring/of special interests) will be coded to a lower-level term (LLT), preferred term (PT), high-level term (HLT), high-level group term (HLGT), and associated primary system organ class (SOC) using the version of Medical Dictionary for Regulatory Activities (MedDRA) currently in effect at Sanofi at the time of database lock.

The occurrence of adverse events (including serious adverse events and adverse events with prespecified monitoring) will be recorded from the time of signed informed consent until the end of the study.

Cardiovascular assessment

All events submitted for cardiovascular adjudication will be listed and summarized, including the final classification results. A swimmer plot including all events classified as cardiovascular, including cardiovascular death, will also be provided.

Furthermore, events classified as cardiovascular will be evaluated according to the following composite endpoints:

- **Major Cardiovascular Adverse Events (MACE):** cardiovascular death, non-fatal myocardial infarction, or non-fatal stroke
- MACE + hospitalization for unstable angina
- Cardiovascular death: death resulting from myocardial infarction, stroke, pulmonary embolism, heart failure, procedure-related death or other cardiovascular cause.
- Hospitalization: for unstable angina, for atrial fibrillation/flutter, for other symptomatic arrhythmias, for transient ischemic attack.
- Other cardio/cerebrovascular events: non-fatal heart failure, peripheral arterial event, pulmonary embolism, non-acute coronary syndrome/myocardial ischemia, others.

Adverse events of special interest (AESI) and other selected AE groupings will be searched based on the criteria in [Table 2](#).

Table 2 - Criteria for adverse events of special interest and other selected AE groupings

AE Grouping	Criteria
AESI	

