2.4.5 Analyses of safety data

The summary of safety results will be presented by treatment group. All safety data collected up to the primary analysis cut-off date (either the IA cut-off date or cut-off date when last patient completes Week 52) will be included.

General common rules

All safety analyses will be performed on the safety population as defined in [Section 2.3.2](#), unless otherwise specified, using the following common rules:

- The baseline value is defined as the last available value before the first dose of IMP.
- The potentially clinically significant abnormality (PCSA) values are defined as abnormal values considered medically important by the Sponsor according to predefined criteria/thresholds based on literature review and defined by the Sponsor for clinical laboratory tests and vital signs and ECG [Appendix A]
- PCSA criteria will determine which patients had at least 1 PCSA during the treatment-emergent adverse event period, taking into account all evaluations performed during the treatment-emergent adverse event period, including nonscheduled or repeated evaluations. The number of all such patients will be the numerator for the on-treatment PCSA percentage

- The treatment-emergent PCSA denominator by group for a given parameter will be based on the number of patients assessed for that given parameter in the treatment-emergent adverse event period by treatment group on the safety population.
- For quantitative safety parameters based on central laboratory/reading measurements, descriptive statistics will be used to summarize results and change from baseline values by visit and treatment group. Summaries will include the endpoint value and/or the worst on-treatment value. The endpoint value is commonly defined as the value collected at the end of treatment. If this value is missing, this endpoint value will be the closest value prior to the end of treatment epoch. The worst value is defined as the nadir and /or the peak post-baseline (up to the end of treatment epoch or EOT) according to the direction (minimum or maximum) of the abnormality as defined in the PCSA list
- The analysis of the safety variables will be essentially descriptive and no systematic testing is planned. Relative risks versus placebo and their 95% confidence intervals may be provided, if relevant
- All safety values including unscheduled measurements will be assigned to the appropriate safety analysis visit window defined in [Section 2.5.3](#).

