2.4.5.1 Analyses of adverse events

Generalities

The primary focus of adverse event reporting will be on treatment-emergent adverse events. Pretreatment and posttreatment adverse events will be described separately.

If an adverse event date/time of onset (occurrence, worsening, or becoming serious) is incomplete, an imputation algorithm will be used to classify the adverse event as pretreatment, treatment-emergent, or posttreatment. The algorithm for imputing date/time of onset will be conservative and will classify an adverse event as treatment emergent unless there is definitive information to determine it is pretreatment or posttreatment. Details on classification of adverse events with missing or partial onset dates are provided in [Section 2.5.2](#).

Adverse event incidence tables will present by SOC, HLT, HLT, and PT, sorted in alphabetical order for each treatment group, the number (n) and percentage (%) of patients experiencing an adverse event. Multiple occurrences of the same event in the same patient will be counted only once in the tables within a treatment phase. The denominator for computation of percentages is the safety population within each treatment group.

Sorting within tables ensures the same presentation for the set of all adverse events within the observation period (pretreatment, treatment-emergent, and posttreatment). For that purpose, the table of all treatment-emergent adverse events presented by SOC and PT sorted by the internationally agreed SOC order and decreasing frequency of PTs within SOCs will define the presentation order for all other tables unless otherwise specified. Sorting will be based on results for the dupilumab 300 mg q2w group.

Risk differences (constructed using the Miettinen and Nurminen method) and hazard ratios (Cox proportional hazards model) for dupilumab versus placebo with corresponding 95% CIs will be provided for the overview table, common TEAEs (PT $\geq 1\%$, 2%, 5% in any intervention

group), and AESIs and other selected AE grouping events table. Participants without an event will be censored at the end of the treatment-emergent period in the Cox model. Forest plots will also be presented.

Analysis of all treatment-emergent adverse events

The following treatment-emergent adverse event summaries will be generated for the safety population.

- Overview of treatment-emergent adverse events, summarizing number (%) of patients with any:
 - Treatment-emergent adverse event

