- All treatment-emergent serious adverse events regardless of relationship and related to IMP, by primary SOC, HLT, and PT, showing the number (%) of patients with at least 1 treatment-emergent serious adverse event, sorted by the internationally agreed SOC order. The other levels (HLGT, HLT, PT) will be presented in alphabetical order.
- All treatment-emergent serious adverse events by primary SOC and PT, showing the number (%) of patients with at least 1 treatment-emergent serious adverse event, sorted by the internationally agreed SOC order and by decreasing incidence of PTs within each SOC in the 300 q2w treatment group.

A listing of all treatment-emergent serious adverse events will be presented

Analysis of all treatment-emergent adverse event(s) leading to treatment discontinuation

- All treatment-emergent adverse events leading to treatment discontinuation, by primary SOC, HLT, and PT, showing the number (%) of patients sorted by the internationally agreed SOC order. The other levels (HLGT, HLT, PT) will be presented in alphabetical order.
- All treatment-emergent adverse events leading to permanent treatment discontinuation or drug interruption, by primary SOC and PT, showing number (%) of patients with at least one TEAE, will be presented by SOC internationally agreed order and by decreasing incidence of PTs within each SOC in the 300 q2w treatment group.

Analysis of Major Cardiovascular Adverse Events (MACE)

- The number and percentage (%) of patients with any treatment-emergent event selected for adjudication will be summarized by primary SOC and PT.
- All events submitted for adjudication will be listed, including the final adjudicated result.
- The number and percentage (%) of patients experiencing a treatment-emergent adjudicated event will be summarized within each treatment group.
- The risk difference (asymptotic 95% CI with continuity correction) will be computed for the dupilumab dose versus placebo. Kaplan-Meier plots to depict the course of onset over time will also be provided.

Analysis of adverse events of special interests (AESI)and other selected AE groupings

- All treatment-emergent adverse events, by selected standardized MedDRA query (SMQ) and PT or by laboratory values (as in ALT elevation), showing the number (%) of patients with at least 1 PT, sorted by decreasing incidence of PTs within each SMQ in the 300 q2w treatment group.
- For each AESI and other selected AE groupings,

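### SAP 2.4.5.1 gives the MACE risk difference a different, unexplained confidence interval whose upper limit is too low when events are very few; aligning it with the AESI tables is a minor, cheap improvement

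*SAP*

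**What the plan says.** SAP 2.1.4.1 defines MACE as "cardiovascular death, non-fatal myocardial infarction, or non-fatal stroke", based on adjudicated events. In SAP 2.4.5.1 the MACE paragraph reads: "The risk difference (asymptotic 95% CI with continuity correction) will be computed for the dupilumab dose versus placebo". Protocol 9.4.2, Table 10, specifies the same interval, so the SAP carries the protocol method forward.

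Earlier in SAP 2.4.5.1, under Generalities, another method is set out: "Risk differences (constructed using the Miettinen and Nurminen method"), together with Cox hazard ratios. These "will be provided for the overview table, common TEAEs", and also for the table of AESIs and other selected AE groupings. Protocol Table 10 specifies no risk difference for AEs or AESIs, so the Miettinen-Nurminen method enters only with the SAP. MACE is not among the AESIs or groupings in SAP Table 2. Neither document says why its interval differs, and SAP 1.6 lists no statistical modifications.

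The MACE paragraph also plans the number and percentage of patients with adjudicated events per arm, a listing of all events sent for adjudication with the final result, and Kaplan-Meier plots. SAP 2.4.5 says of safety in general: "The analysis of the safety variables will be essentially descriptive and no systematic testing is planned".

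**The concern.** MACE may well be infrequent in this trial, and cardiovascular events are singled out for independent adjudication and regular DMC attention (protocol 2.3). A Wald interval estimates its standard error from the observed proportions. When an arm has no events, that arm contributes nothing to the standard error, and the fixed continuity correction has to supply the missing uncertainty. In a safety table the upper limit for active minus placebo is what a reader uses to judge how large an excess has not been ruled out. If that limit is too low at very small counts, the table reassures more than the data allow. Two methods in one section also mean that the same counts would get one interval in the MACE table and another in an AESI table.

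**Working it through.** **Inputs.** Planned size: "A total of approximately 924 patients with COPD will be randomized to two treatment arms (462 patients/arm"), used here as the treated number per arm (assumption). Interval for MACE: "asymptotic 95% CI with continuity correction"; its exact form is not given, so the standard correction (1/n1+1/n2)/2 is assumed. MACE risks: none in the documents, so the values below are illustrative.

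**The plan's own figure.** There is none for MACE. The 462 per arm comes from the primary endpoint (SAP 1.3: placebo rate 1.5, dupilumab rate 1.125, dispersion 1, mean duration 0.95 year). Variance of the log rate ratio = [1/(1.5×0.95) + 1/(1.125×0.95) + 2]/462 = (0.7018 + 0.9357 + 2)/462 = 0.00787, so SE = 0.0887. Then |ln 0.75|/SE = 0.2877/0.0887 = 3.24, and 3.24 − 1.96 = 1.28 gives 90% power. The stated figure reproduces.

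**Formulas for the risk difference d = p1 − p0.**
- Planned: d ± {1.96·√[p1(1−p1)/n + p0(1−p0)/n] + 1/n}. With n = 462 the correction is 1/462 = 0.216 percentage points.
- Miettinen-Nurminen (MN): the values of d for which the score statistic, with restricted maximum-likelihood variance times N/(N−1) and N = 924, lies within ±1.96.

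**By hand at the lowest counts.**
- 0 vs 0, planned: SE = 0, leaving only ±0.216, that is ±0.22.
- 0 vs 0, MN: the restricted estimates are d and 0, so d² = 3.84·d(1−d)/462·(924/923). With k = 3.8415×1.00108/462 = 0.00832, d = k/(1+k) = 0.83 points.
- 1 vs 0, planned upper limit: 0.216 + 1.96×0.216 + 0.216 = 0.86. The MN upper limit is 1.22.

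**Intervals (percentage points, dupilumab vs placebo events).**

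| Counts | Planned | MN | Fisher two-sided p |
|---|---|---|---|
| 0 vs 0 | −0.22 to 0.22 | −0.83 to 0.83 | 1.00 |
| 5 vs 0 | −0.08 to 2.24 | 0.25 to 2.51 | 0.062 |
| 6 vs 0 | 0.05 to 2.55 | 0.47 to 2.81 | 0.031 |
| 7 vs 1 | −0.11 to 2.71 | 0.14 to 2.90 | 0.069 |
| 8 vs 1 | 0.04 to 2.99 | 0.32 to 3.19 | 0.038 |
| 9 vs 2 | −0.10 to 3.13 | 0.14 to 3.28 | 0.064 |

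At 5 vs 0 the planned interval is no narrower than MN (width 2.32 against 2.26). It is shifted downwards, so its upper limit is lower.

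**Coverage, by full enumeration of both binomials.**

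| True risks | Planned | MN |
|---|---|---|
| 0.5% vs 0.5% | 99.3% | 95.5% |
| 1% vs 1% | 98.0% | 95.7% |
| 2% vs 2% | 97.2% | 95.1% |
| 0.5% vs 0.1% | 93.0% | 97.3% |
| 0.5% vs 0% | 90.1% | 99.1% |
| 0.25% vs 0% | 68.5% | 99.3% |

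The last row can be checked directly. With risks of 0.25% and 0%, the chance of no events in either arm is 0.9975^462 = 31.5%. The planned interval is then ±0.22 and misses the true 0.25; 100 − 31.5 = 68.5. At 0.5% vs 0.1%, 7.0% of planned intervals lie wholly below the true excess and 0.04% wholly above, so nearly all misses understate the risk.

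For every pair of risks on a grid from 0.25% to 3% in both arms, planned coverage is at least 96.3%. At 1% vs 0% both methods give 94.5%. Real under-coverage therefore needs one risk near zero and the other small.

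**When zero is excluded.** For 0 to 10 placebo events, the planned interval needs one more dupilumab event than MN to exclude zero, or two more when placebo has 0, 6 or 8.

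**The case against.** A reader might infer that the planned interval would hide a cardiovascular imbalance, that it is badly calibrated for rare events in general, or that every other AE is analysed with MN. The documents and figures support none of these.

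- *Hiding an imbalance.* The difference is one or two events in when zero is excluded. At 5 vs 0, 7 vs 1 and 9 vs 2 Fisher's p is 0.06 to 0.07, so the planned interval agrees with the exact test there, and MN excluding zero is not firm evidence of harm. Arm-level counts, the listing and the Kaplan-Meier plots are planned regardless, and SAP 2.1.4.1 adds a swimmer plot of events classified as cardiovascular. Safety analysis is descriptive, with no rule tied to this interval.
- *Calibration.* From 0.25% to 3% in both arms the planned interval is conservative. Protocol 2.3 calls cardiovascular disease frequent in COPD, so a placebo MACE risk near zero may not be the likeliest case.
- *Scope.* MN is specified only for the tables named in SAP 2.4.5.1. The SOC/PT, SAE, discontinuation and death tables specify only numbers and percentages.

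The method is also prespecified in the protocol, so following it is no error. All of this stands and keeps the point minor. It does not explain why one section uses two methods, and it does not repair the upper limit at the lowest counts.

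**Conclusion.** The point holds as a minor inconsistency with a small technical cost. The planned MACE interval errs in both directions: it over-covers by about 2 to 4 percentage points at equal risks of 0.5% to 2%, and its upper limit is too low when one arm has almost no events (0.22 against 0.83 points at 0 vs 0; 0.86 against 1.22 at 1 vs 0). The second matters more for safety, because it understates the largest excess not ruled out. No trial decision changes.

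The figures rest on three assumptions: 462 treated per arm, the standard form of the correction, and illustrative MACE risks. How far the low-count problem matters depends on the actual MACE frequency, which the documents do not give.

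**What to change.** In SAP 2.4.5.1, MACE paragraph, replace the continuity-corrected asymptotic interval with the Miettinen-Nurminen interval already specified for the AESIs, and record the change from protocol Table 10 in SAP 1.6. The edit is one phrase plus one line in SAP 1.6, and the method is already needed for the other AE tables. The downside is a minor departure from the method stated in the protocol.

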AESI and other AE groupings	Incidence of each type of AESI and other AE groupings will be tabulated by treatment group. For each type of AESI, the following analysis will be generated. • A summary of the number (%) of patients with - Any TEAE. - Any SAE (regardless of treatment-emergent status). - Any treatment-emergent SAE. - Any AE leading to death. - Any TEAE leading to death. - Any TEAE leading permanent treatment discontinuation. - Any TEAE related to IMP reported by Investigator. - Number of patients with the TEAE per 100 patient-years. - Any TEAE by maximum intensity, corrective treatment, and final outcome. • Kaplan-Meier (K-M) estimates of probability of having at least one TEAE at specific time points, and K-M curve to depict the course of event onset over time. The method to identify AESIs and other AE groupings will be specified in the SAP.
Death	 The following deaths summaries will be generated: Number (%) of patients who died by study period (TEAE, on-study) summarized on the safety population by treatment received. Death in nonrandomized patients or randomized and not treated patients. Treatment-emergent AE leading to death (death as an outcome on the AE eCRF page as reported by the Investigator) by primary SOC, HLGT, HLT, and PT showing number (%) of patients sorted by internationally agreed order of SOC and alphabetic order of HLGT, HLT, and PT.

28-Oct-2023 Version number: 1

Endpoint	Statistical Analysis Methods
Laboratory parameters	Results and change from baseline for the parameters will be summarized by treatment group for baseline and each post baseline time point, endpoint, minimum and maximum value. Summary statistics will include number of patients, mean, standard deviation, median, Q1, Q3, minimum, and maximum.
	The following definitions will be applied to laboratory parameters.
	 The potentially clinically significant abnormality (PCSA) values are defined as abnormal values considered medically important by the Sponsor according to predefined criteria/thresholds based on literature review and defined by the Sponsor for clinical laboratory tests. PCSA criteria will determine which patients had at least 1 PCSA during the on-treatment period, taking into account all evaluations performed during the on-treatment period, including unscheduled or repeated evaluations. The number of all such patients will be the numerator for the
	on-treatment PCSA percentage.

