2.1.4 Safety endpoints

The safety analysis will be based on the reported adverse events and other safety information, such as clinical laboratory data, vital signs, ECG and physical examination.

Observation period

The observation period will be divided into 4 epochs:

- The **screening** epoch is defined as the time from the signed informed consent date up to the time prior to first administration of the IMP.

- The **treatment** epoch is defined as the time from the first administration of the IMP to the last administration of the IMP + 14 days.
- The **residual treatment** epoch is defined as the time from the last administration of the IMP +15 days to the last administration of the IMP + 98 days.

The treatment-emergent adverse event period will include both **treatment** and **residual treatment** epochs.

- The **posttreatment** epoch is defined as the period of time starting the day after the end of the treatment-emergent adverse event period up to the end of the study (defined as last protocol planned visit or the resolution/stabilization of all serious adverse events and adverse events with pre-specified monitoring).
- The on-study observation period is defined as the time from start of treatment until the end of the study (defined as last protocol planned visit or lost to follow-up or the resolution/stabilization of all serious adverse events and adverse events with pre-specified monitoring).

Safety events adjudication

Adjudication will be performed by experts independent of sponsor for the evaluation of whether deaths, cardiovascular SAEs and respiratory SAEs meet criteria for cardiovascular assessment endpoints. A confirmatory adjudication will occur for AECOPD exacerbations. Adjudicators will adjudicate these events in a consistent and unbiased manner throughout the study.

The goal of the adjudication is to ensure that all events reported by the site are judged uniformly, using pre-specified criteria by a group independent of the Sponsor. Adjudication Committee members will be blinded to treatment allocation. Adjudication Committee members' responsibilities and the process for data review are described in the AC Charter/Manual of Operation.

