2.4.3 Extent of investigational medicinal product exposure and compliance

The extent of IMP exposure and compliance will be assessed and summarized by actual treatment within the safety population (Section 2.3.2).

2.4.3.1 *Extent of investigational medicinal product exposure*

The extent of IMP exposure will be assessed by the duration of IMP exposure.

Duration of IMP exposure is defined as last dose date – first dose date + 14 days, regardless of unplanned intermittent discontinuations (see Section 2.5.3 for calculation in case of missing or incomplete data). Duration of IMP exposure will be summarized descriptively as a quantitative variable (number, mean, SD, median, minimum, and maximum). In addition, duration of treatment exposure will also be summarized categorically by numbers and percentages for each of the following categories and cumulatively according to these categories:

- >0 and \leq 2 weeks
- >2 and \leq 4 weeks
- >4 and \leq 8 weeks
- >8 and \leq 12 weeks
- >12 and \leq 16 weeks
- ...
- ...
- >48 and \leq 52 weeks
- >52 weeks and \leq 52 weeks + 3 days
- >52 weeks + 3 days

Additionally, the cumulative duration of treatment exposure will be provided, defined as the sum of the duration of treatment exposure for all patients, and will be expressed in patient years.

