 - Number (%) of patients with any specific TEAE
 - Number (%) of patients with any specific serious AE (regardless of treatment emergent status)
 - Number (%) of patients with any specific treatment emergent serious AE
 - Number (%) of patients with any specific AE leading to death
 - Number (%) of patients with any specific TEAE leading to permanent study drug discontinuation

- Number (%) of patients with any specific TEAE related to IMP reported by investigator
- Number (%) of patients with any specific TEAE by maximum intensity, corrective treatment, and final outcome
- Number of any specific TEAE adjusted by the exposure duration
- Number of patients with any specific TEAE adjusted by the exposure duration at risk. For each specific TEAE, Kaplan-Meier estimates of cumulative incidence at Week 12, 24, 36 and 52 and K-M plot may be provided to depict the course of onset over time if the number of events is large enough.
- Number (%) of patients with injection site reactions by the related injection.
- Number (%) of patients with different number of injection site reactions.
- In addition, AESIs reported by the investigator in CRF will be summarized separately.

Analysis of pretreatment adverse events

- All pretreatment adverse events by primary SOC and PT, showing the number (%) of patients with at least 1 pretreatment adverse event, sorted by the internationally agreed SOC order and decreasing incidence of PTs within each SOC in the 300 q2w treatment group.
- All serious pretreatment adverse events by primary SOC and PT, showing the number (%) of patients with at least 1 pretreatment adverse event, sorted by the internationally agreed SOC order and decreasing incidence of PTs within each SOC.
- All pretreatment adverse events leading to permanent treatment discontinuation by primary SOC and PT, showing the number (%) of patients, sorted by the internationally agreed SOC order and decreasing incidence of PTs within each SOC.
- All pretreatment adverse events leading to death by primary SOC and PT, showing the number (%) of patients, sorted by the internationally agreed SOC order and decreasing incidence of PTs within each SOC.
- If only a few patients have pretreatment adverse events leading to permanent treatment discontinuation, a listing will be presented instead of the summary table above.

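### As the SAP's definitions stand, the exposure-adjusted AESI event rate counts events to last dose + 98 days but divides by exposure that ends at last dose + 14 days

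*SAP*

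**What the plan says.** **The two rates.** SAP 2.4.5.1 lists two exposure-adjusted summaries for each AESI and other selected grouping. One is an event count: "Number of any specific TEAE adjusted by the exposure duration". The other is a patient count: "Number of patients with any specific TEAE adjusted by the exposure duration at risk". The section defines neither denominator and gives no cross-reference. Table 10 in Protocol 9.4.2 has only the patient-count form, "Number of patients with the TEAE per 100 patient-years", and names no time window.

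**The numerator window.** SAP 2.1.4 says "The treatment-emergent adverse event period will include both" the treatment epoch and the residual treatment epoch. The residual epoch is the "time from the last administration of the IMP +15 days to the last administration of the IMP + 98 days". Protocol 9.4.2 gives the same end point for the TEAE period.

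**The exposure definition.** SAP 2.4.3.1 states: "Duration of IMP exposure is defined as last dose date – first dose date + 14 days, regardless of unplanned intermittent discontinuations". It then says "the cumulative duration of treatment exposure will be provided, defined as the sum of the duration of treatment exposure for all patients", in patient-years. SAP 2.5.3 uses the term exposure duration for this dose-based quantity: it is left missing when the last-dose date is missing.

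**The other clock in the same section.** The Cox model in SAP 2.4.5.1, which also covers the AESI table, censors event-free participants at the end of the treatment-emergent period, that is, on the + 98-day window.

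**The concern.** A rate per patient-year needs numerator and denominator to cover the same time. A programmer who follows the SAP would take the exposure duration from 2.4.3.1, because there is no other, and divide into it TEAEs that include those from days 15 to 98 after the last dose. Those 84 days can add events but add no time.

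The absolute event rates for serious infection, hypersensitivity, keratitis and the other groupings would then be too high for the period in which the events were collected. They would also rest on a different time base from the hazard ratios for the same events. And they could drift between database locks: once a patient has stopped dosing, the denominator is fixed while tail events continue to be added. Safety data for the primary analysis are cut at the interim or last-patient Week 52 date (SAP 2.4.5), whereas later data may run to Week 64 (SAP 4).

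**Working it through.** Neither document states an adverse event rate or a safety patient-year total, so there is no planned figure to reproduce. The check is arithmetic on the windows.

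**Inputs**
- Exposure = last dose - first dose + 14 days (SAP 2.4.3.1).
- TEAE window = last dose - first dose + 98 days (SAP 2.1.4, Protocol 9.4.2).
- A completer's last dose is at Week 50, day 350 after the first dose (Protocol 1.3.1, footnote on IMP administration).
- Assumed, not in the documents: a constant event rate through the tail, the early-stopping fractions and the accrual pattern.

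**1. One patient, full follow-up.** With D days from first to last dose, the window ratio is (D + 98)/(D + 14).

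| Last dose | TEAE days / exposure days | Ratio |
|---|---|---|
| Week 50 | 448/364 | 1.23 |
| Week 24 | 266/182 | 1.46 |
| Week 12 | 182/98 | 1.86 |
| Week 0 (one dose) | 98/14 | 7.0 |

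**2. One arm, full follow-up.** A group rate is summed events over summed time, and every patient adds 84 days to the window, so the ratio is 1 + 84/(mean exposure).

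| Assumed early stopping | Mean exposure (days) | Ratio |
|---|---|---|
| None | 364 | 1.231 |
| 10%, last dose spread evenly over Weeks 0-48 | 0.9 × 364 + 0.1 × 182 = 345.8 | 1.243 |
| 20%, same spread | 0.8 × 364 + 0.2 × 182 = 327.6 | 1.256 |
| 20%, all after one dose | 0.8 × 364 + 0.2 × 14 = 294 | 1.286 |

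The second row equals 0.95 × 364 days, in line with the average treatment duration of 0.95 year assumed for the sample size (SAP 1.3).

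**3. One arm at the planned cut-offs.** With accrual assumed uniform over 1.5 to 3.5 years and no early stopping, part of the tail is still unobserved:
- Interim, information fraction 0.92: 1.15 to 1.19.
- Interim, information fraction 0.965: 1.17 to 1.20.
- Last-patient Week 52: 1.21 to 1.22.

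**4. Event rate in the tail.** If the tail rate is r times the on-treatment rate, a completer's inflation is 1 + 84r/364. That gives 1.23 at r = 1, 1.12 at r = 0.5 and 1.00 at r = 0.

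**5. Between arms, full follow-up.**
- 10% v 20% early stopping, spread as in step 2: 1.2564/1.2429 = 1.011.
- 5% v 15% stopping after a mean of 8 doses (112 days of exposure): (435.4/351.4) v (410.2/326.2) = 1.239 v 1.258, ratio 1.015.

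**The case against.** The best counter-argument is that SAP 2.4.5.1 never says its denominator is the + 14-day duration. The mismatch comes from joining that section to 2.4.3.1, where the definition serves the exposure table. On this view the defect is an undefined term in a descriptive table: SAP 2.4.5 plans no systematic testing of safety variables, and the planned AESI comparisons are risk differences and hazard ratios, not ratios of these rates.

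The first part does not remove the point for the event-count rate. SAP 2.5.3 uses the same term for the dose-based quantity and no other meaning is offered, so following the SAP produces the mismatch. The second part stands as a limit on the consequence: no tested hypothesis depends on this.

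Three stronger readings are tempting and should not be drawn.
- **That both rates are inflated.** The patient-count rate is adjusted by exposure duration at risk, which the SAP does not define. Given the Cox censoring rule in the same section, it may already mean time to last dose + 98 days. That rate lacks a definition; inflation is not shown.
- **That rates are inflated several-fold in early stoppers.** The factor of 7 is the window ratio for one patient who had one dose. No planned output reports a rate for early stoppers, and an arm in which 20% stop after one dose reaches only 1.29.
- **That the comparison between arms is materially biased.** The documents give no differential discontinuation, and assumed differences of 10 percentage points move the ratio by 1-1.5%.

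It is also fair that one multiplier does not suit every AESI. Severe injection site reactions and symptomatic IMP overdose are tied to dosing, so few would be expected in the tail and their inflation would be near zero.

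**Conclusion.** The point holds for the AESI event-count rate. As the SAP's definitions stand, its denominator window is up to 84 days shorter than its numerator window.

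With full follow-up and a constant event rate, absolute rates are overstated by about 23-29% at arm level. The lower end needs no assumption about early stopping; the upper end assumes that 20% of the arm stops after one dose. At the interim or last-patient Week 52 cut-off the overstatement is about 15-22%, which depends on the accrual assumed. It is smaller where events are less frequent after dosing stops, or where patients die or withdraw during the tail. Between-arm distortion is about 1%.

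The harm is therefore to the absolute rates, to their consistency across database locks, and to their agreement with the Cox analysis of the same events. For the patient-count rate the finding is only that its denominator must be defined.

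**What to change.** In SAP 2.4.5.1:
- Define the event-rate denominator as observed time in the treatment-emergent period: first dose to the earliest of last dose + 98 days, last contact, death or data cut-off.
- State that exposure duration at risk is the same time, stopped at the first event of that type. This matches the Cox censoring rule in the section and supplies the window that Protocol Table 10 leaves open.
- Keep the SAP 2.4.3.1 duration for the exposure table only.

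The cost is a sentence or so of SAP text and one derived variable. Data collection and trial conduct do not change. For events that continue into the tail, event rates will come out lower than under the present definitions.
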